### **9.2.2 Adverse Event Overview**

Overall summary of TEAEs will be provided on a per-participant level for TEAEs, treatment-related TEAEs, TESAEs, treatment-related TEAEs, deaths, and TEAEs leading to discontinuation.

### **9.2.3 Treatment-Emergent Adverse Events by SOC and/or PT**

AEs will primarily be assessed through the analysis of AEs reported in the 48 hours following the administration of each study intervention. A supportive analysis will include AEs reported within 30 days after the study intervention (and before the next intervention if any). Unique participants reporting AEs will be summarized in the following AE categories by treatment and total for the safety population in double-blind treatment period.

- TEAEs by SOC and PT.
- TEAEs by SOC, PT and severity. If more than 1 AE is coded to the same PT for the same participant, the participant will be counted only once for that PT using the maximum severity for the summarization by severity. If the severity of a TEAE is missing, the maximum severity will be assigned to the event for the summarization by severity. The value will be displayed as missing in the data listing.
- Treatment-related TEAEs by SOC and PT. If more than 1 AE is coded to the same PT for the same participant, the participant will be counted only once for that PT using the closest causal relationship to treatment for the summarization by causal relationship. If the relationship to the study intervention is missing for a TEAE, the event will be considered related to the study intervention for the summarization. The value will be displayed as missing in the data listing.
- The incidence of common ( $\geq 2\%$  [after rounding] of participants in either study intervention) TEAEs will be summarized by descending frequency in the ubrogepant group.

#### **9.2.4 SAEs (Including Deaths) and Adverse Events Leading to Study Drug Discontinuation**

TEAEs leading to discontinuation and TESAEs will be summarized by SOC and PT. Listings of all TEAEs, SAEs, and AEs leading to discontinuation will be provided.

#### **9.2.5 Adverse Events of Special Interest**

Adverse events of special interest will be summarized by SOC and PT recorded on case report form (CRF) as of special interest.

### **9.3 Analysis of Laboratory Data**

#### **9.3.1 Clinical Laboratory Parameters**

Descriptive statistics for clinical laboratory values (in SI units) at baseline and changes from baseline at each assessment time point will be presented by study intervention for

each clinical laboratory assessment. An assessment will be assigned to the most recently administered study intervention.

- Hematology: Hemoglobin; hematocrit; red blood cell count; red blood cell indices (mean corpuscular volume, mean corpuscular hemoglobin, mean corpuscular hemoglobin concentration); white blood cell count, including differential (neutrophils, lymphocytes, monocytes, eosinophils, and basophils); platelet count
- Chemistry: Sodium, potassium, chloride, bicarbonate, glucose, blood urea nitrogen, creatinine, total bilirubin, alkaline phosphatase, aspartate aminotransferase, alanine aminotransferase, lactate dehydrogenase, creatine kinase, total protein, albumin, calcium, phosphorus, uric acid, total cholesterol, HDL, LDL, total triglycerides, eGFR (calculated by the central lab)
- Urinalysis: Specific gravity, pH.

Shift tables from baseline to end of study for these clinical laboratory parameters will be presented by study intervention for the following categories: low, normal, and high, which are categorized by the laboratory vendor based on reference ranges.

### **9.3.2 Potentially Clinically Significant Laboratory Findings**

Clinical laboratory test values will be considered potentially clinically significant (PCS) if they meet either the lower-limit or higher-limit PCS criteria listed in Table C-1.

The number and percentage of participants who have at least one PCS post-baseline clinical laboratory value will be tabulated by study intervention. The percentages will be calculated based on the denominator of the number of participants with available non-PCS baseline values and at least one post-baseline value and the numerator of the number of participants with non-PCS baseline value and at least one PCS post-baseline value. In addition, a listing of all AEs occurring in participants who have PCS clinical laboratory test values will be provided.

A listing of participants with PCS postbaseline values will be provided for the safety population.

### **9.3.3 Hepatic Laboratory Abnormalities**

The number and percentage of participants meeting each of the criteria provided in Table C-2 for postbaseline hepatic laboratory abnormalities will be summarized by study intervention group. The percentages will be calculated relative to the number of participants with at least 1 available postbaseline assessment. The numerator will be the total number of participants having at least 1 postbaseline value that meets the specific category.

A listing of participants with hepatic laboratory abnormalities will be provided for the safety population.

### **9.4 Analysis of Vital Signs**

Descriptive statistics for vital signs (systolic and diastolic blood pressures, pulse rate, respiratory rate, and temperature) at baseline, postbaseline, and changes from baseline values at each postbaseline timepoint will be presented by study intervention. An assessment will be assigned to the most recently administered study intervention. Vital sign values will be considered PCS if they meet both the observed value criterion and the change from baseline value criterion, if both criteria are available, or meet either the observed value criterion or the change from baseline value criterion that will be detailed in Table C-3.

The number and percentage of participants who have PCS postbaseline vital sign values will be calculated relative to the number of participants who have available baseline or non-PCS baseline (for parameters with only the observed value criterion) values and at least 1 postbaseline assessment. The numerator will be the total number of participants with at least 1 PCS postbaseline value during the qualifying prodrome event.

A supportive listing of participants with PCS postbaseline values will be provided.

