6.3.1. Qualifying Prodrome Event

For both the screening and double-blind treatment periods, a *qualifying prodrome event* is defined as an event in which the participant experiences a clinically identifiable prodrome with all the following conditions met:

- Headache is not currently present
- The participant has not had a headache in the previous 48 hours
- Treatments for acute headache (eg, ibuprofen, acetaminophen, triptan, Excedrin®) have not been taken in the previous 48 hours
- The participant is confident that a headache will inevitably follow within 1 to 6 hours after experiencing the qualifying prodrome event
- The participant is able to complete the eDiary for the next 8 hours

Participants who meet all of the initial study entry criteria at the Screening Visit (Visit 1) will be dispensed an eDiary to record their qualifying prodrome events within 60 days. At Visit 2, if they qualify, participants will be randomized, provided with double-blind study intervention to treat the first qualifying prodrome event, and redispensed the eDiary to record the first qualifying prodrome event. At Visit 3, participants will be provided with double-blind study intervention to treat the second qualifying prodrome event and redispensed the eDiary to record the second qualifying prodrome event.

For the double-blind treatment period, it is recommended to treat qualifying prodrome events that occur in the morning or early afternoon so that assessments can be collected in the eDiary during waking hours.

Study participants will have up to 60 days to treat 2 qualifying prodrome events at home with study intervention during the double-blind treatment period (between Visit 2 and Visit 4). Participants unable to treat 2 qualifying prodrome events within this time will be discontinued from the study.

Please refer to Section 6.5.3 for details regarding rescue medication use.

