This visit will occur 4 days (-2/+4 days) after double-blind study intervention is taken for the first qualifying prodrome event. It can occur as early as 2 days after taking double-blind study intervention (after the 48 hour assessment has been completed) and as late as 8 days after taking

double-blind study intervention; however, participants should be encouraged to come in for this visit as soon as possible after completing their 48 hour assessments.

The following study procedures will be carried out at the Posttreatment Visit (Visit 3):

- Register the participant's visit in the IWRS
- Collect vital sign measurements (sitting and standing systolic and diastolic BP, sitting and standing pulse rate, respiration rate, temperature, and weight)
- Review concomitant medication
- Review and assess AEs
- Assess C-SSRS on eTablet (the *Since the Last Visit* assessment of the C-SSRS will be completed)
- Perform urine pregnancy test (for WOCBP only)
- Review eDiary entries and ensure all questions and assessments were completed. Ensure the eDiary is functioning appropriately, sending data as programmed, and the participant continues to understand how to use the eDiary. Complete retraining if needed. Redispense the eDiary back to the participant.
- Collect side effects diary. Review the side effects listed on the diary and enter identified AEs in EDC. Provide participant with new side effects diary.
- Collect study intervention blister package; review compliance against the information collected in the eDiary.
- Obtain the kit number for study intervention in IWRS and dispense a blister card with the study intervention for the second qualifying prodrome event. Review dosing instructions with the participant again if needed.

For those participants participating in the optional PK substudy:

- Collect the DBS samples that the participant collected at home and ensure that the collection dates and times are recorded in the eDiary
- Review collection timing, handling, and storage of DBS samples that will be collected at home after the second qualifying prodrome event. Provide the participant with the supplies for PK sample collection.

The first and second qualifying prodrome events must be 2 separate and distinct events that are at least 7 days apart.

Posttreatment Visit (Visit 4) After Treatment of Second Qualifying Prodrome Event/ ET Visit

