8.2.2. Vital Signs

Vital sign measurements, including sitting and standing BP, sitting and standing pulse rate, respiratory rate, temperature, body weight, and height (at Visit 1 only), will be performed at every visit.

Sitting and standing BP and pulse rate will be determined as follows: BP and pulse measurements will be performed after the participant sits quietly for 5 minutes, followed by a second set of measurements taken after the participant stands for 3 minutes (but no longer than 10 minutes).

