9.4.2.3. Vital Signs

Descriptive statistics for vital signs (sitting and standing systolic and diastolic BP, sitting and standing pulse rate, respiration rate, temperature, weight, and body mass index) at baseline and changes from baseline at postdose assessment will be presented by study intervention.

Vital signs values will be considered to be potentially clinically significant if they meet both the observed-value criteria and the change-from-baseline-value criteria that will be detailed in the SAP. The number and percentage of participants who have potentially clinically significant postbaseline vital sign values will be tabulated by study intervention. The assessment will be presented in the last study intervention the participant received. The percentages will be calculated relative to the number of participants who have available nonpotentially clinically significant baseline values and at least 1 postbaseline assessment. The numerator will be the total number of participants with at least 1 potentially clinically significant postbaseline value. A supportive listing of participants with potentially clinically significant postbaseline values will be provided for the safety population.

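### SAP 9.4 ties the vital-sign PCS numerator to the qualifying prodrome event, a window in which, as the protocol defines it, no vital signs are scheduled

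*SAP*

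**What the plan says.** SAP 9.4 (Analysis of Vital Signs) defines the PCS numerator as follows: "The numerator will be the total number of participants with at least 1 PCS postbaseline value during the qualifying prodrome event". The denominator in the same paragraph requires an available baseline (a non-PCS baseline for parameters that have only an observed-value criterion): "values and at least 1 postbaseline assessment". It mentions no event. Earlier in the section, each assessment is assigned to the most recently administered study intervention.

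Protocol 9.4.2.3 defines the numerator for the same table without the closing phrase: "The numerator will be the total number of participants with at least 1 potentially clinically significant postbaseline value".

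Protocol 6.3.1 makes the qualifying prodrome event a defined term, "defined as an event in which the participant experiences a clinically identifiable prodrome with all the following conditions met", and the first condition is that headache is not currently present. Participants have up to 60 days "to treat 2 qualifying prodrome events at home with study intervention during the double-blind treatment period". Under protocol 8.2.2, vital signs "will be performed at every visit". On Visit 3, protocol Section 8 says: "This visit will occur 4 days (-2/+4 days) after double-blind study intervention is taken for the first qualifying prodrome event". It gives Visit 4 the same window after the second dose.

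**The concern.** The numerator and denominator use different windows, and the numerator's window appears to contain no planned measurement. A programmer who applies the protocol's definition would produce a by-treatment safety table with no PCS finding from any scheduled visit, in either treatment. A reader could take that for evidence of no vital-sign effect, when it would only reflect when the cuff was applied.

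A second, independent mismatch concerns who is counted. SAP 9.3.2 (laboratory) and 9.6.1 (ECG) limit the numerator explicitly to participants with a non-PCS baseline. SAP 9.4 does not, although for some parameters its denominator has that limit.

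**Working it through.** The documents give no expected PCS count, so there is no figure to reproduce. The check sets the vital-sign schedule against the possible meanings of the event window.

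**Inputs**
- Vital-sign row of the Schedule of Activities (protocol Table 1-1): marked at Visits 1, 2, 3 and 4, blank in both treatment-day columns.
- Window for Visits 3 and 4 (protocol Section 8 and Table 1-1): 4 days after dose, −2/+4 days, and not before the 48-hour assessment is complete.
- Last eDiary assessment of a treated event: 48 hours after dose.

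**Timing of scheduled postdose vital signs**
- Earliest: (4 − 2) days × 24 = 48 hours, and only after the 48-hour entry.
- Latest: (4 + 4) days × 24 = 192 hours.

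**Scheduled values that can enter the numerator**

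| Meaning of the event | Scheduled postdose vital signs inside it |
|---|---|
| Prodrome with headache absent, as defined in protocol 6.3.1 | None |
| Stretched to the whole 48-hour diary follow-up | None (earliest visit follows the 48-hour assessment) |
| Crossover period: from one dose until the next dose or study exit | All Visit 3 and Visit 4/ET values |

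Under the first two readings, scheduled visits contribute 0 to the count for each of the seven Table C-3 parameters: systolic pressure, diastolic pressure, pulse rate, weight, and the three orthostatic changes. The denominator meanwhile includes everyone with a usable baseline and any postbaseline assessment.

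**Comparison with the parallel rules.** The numerators in protocol 9.4.2.3 and in SAP 9.3.2 (laboratory), 9.3.3 (hepatic) and 9.6.1 (ECG) contain no event restriction. SAP Appendix F, which lists changes to protocol-planned analyses, covers the imputation sequence, the Kaplan-Meier handling of rescue medication and the predose baseline covariates. It does not mention this change. The phrase therefore looks like a drafting slip and not a decision.

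**Numerator against denominator.** In Table C-3 the three orthostatic parameters have an observed-value criterion only, so their denominator requires a non-PCS baseline. Take a participant whose orthostatic systolic change is −20 mm Hg at baseline and again at Visit 4. The criterion is ≤ −20, so this participant is PCS both times. The denominator excludes the participant, but nothing in the numerator sentence does.

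**The case against.** The best defence is that the SAP also uses qualifying prodrome event as a label for the crossover period. The first and second events head the columns of the treatment-sequence table in SAP 2.3. SAP 8.3.3 equates the two events with the two repeated measurements, and SAP Table 3 treats a missing prodrome event much like a missing period. Together with the assignment rule in SAP 9.4 itself, the sentence can be read so that Visit 3 values belong to the first event and Visit 4 values to the second. This stands as a possible reading. It does require leaving the protocol's definition, though, and the SAP's safety section already has its own word for a period (Period 1 and Period 2 in SAP 9.2.1). A count that is either empty of scheduled data or complete, depending on who reads the sentence, needs correcting either way.

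Three stronger inferences are tempting, and the documents do not support them:

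- **No vital signs can fall inside an event.** The documents show only that none are scheduled there. The early-termination visit includes vital signs with no stated minimum time after dosing, and protocol Section 8 allows additional examinations at unscheduled visits.
- **The table must show zero throughout.** That does not follow, because such off-schedule values could enter and because the period reading exists.
- **Every PCS change would be hidden.** SAP 9.4 also provides a listing of participants with PCS postbaseline values and descriptive statistics by intervention, neither restricted to the event. Abnormal vital signs that the investigator judges clinically significant are adverse events under protocol 10.3.1.

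On the orthostatic mismatch, it is fair to say that protocol 9.4.2.3 has the same feature: a non-PCS-baseline denominator and an unrestricted numerator. The wording is inherited, so the proper comparators are the SAP's own laboratory and ECG rules. The inconsistency with those rules remains.

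**Conclusion.** Wrong as written, of minor severity. With the protocol's definition of a qualifying prodrome event, the SAP 9.4 numerator counts no scheduled vital-sign value for any Table C-3 parameter in either treatment. The phrase also conflicts with protocol 9.4.2.3, departs from the SAP laboratory and ECG rules, and is not declared in Appendix F. The conclusion assumes that the defined term carries its protocol meaning and that visits keep to their windows. If event means crossover period, the window problem disappears.

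The effect is limited to the PCS summary table. Within SAP 9.4, that table matters most for weight and orthostatic change: the section's descriptive list does not name them, so the PCS count is the only by-treatment summary it describes for them (protocol 9.4.2.3 does list weight among its descriptive statistics). The baseline mismatch affects the three orthostatic parameters only. No size can be given for it without data.

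**What to change.** Delete the last five words of the numerator sentence in SAP 9.4 and restate the rule along these lines: *for each study intervention, count the participants in the denominator who have one or more PCS postbaseline values assigned to that intervention, meaning the one most recently administered; Visit 3, Visit 4/ET and unscheduled values all count.*

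The new sentence should rest on the assignment rule already in SAP 9.4 and should not map Visit 3 to the first dose and Visit 4 to the second. Participants who treat only one event still have vital signs at Visit 4/ET, and a rule tied to the second dose would drop those values.

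The cost is one sentence in the SAP, with no new data collection. Numerator and denominator then draw on the same participants, and the protocol's unrestricted counting of postbaseline values is restored.

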The prodrome represents the beginning of a migraine attack and there is evidence for alterations in hypothalamic and brainstem function during the prodrome, which can be demonstrated by functional imaging and electrophysiological methods (Karsan 2018). The headache phase is due to activation of trigeminal sensory neurons, many of which express CGRP, that innervate pain sensitive intracranial structures including the eye, dura, meningeal vessels, and dural venous sinuses. During the headache phase, CGRP is released pathologically from these sensory nerves in the meninges and from their central projections to the spinal trigeminal nucleus, and this can be detected as increased levels of CGRP in the cranial venous outflow (Goadsby 2017, Messlinger 2018).

The goal of this study is to administer ubrogepant during the prodrome so that it is 'on board' as the headache phase pathophysiology emerges, with the ultimate objective of preventing or ameliorating the headache phase. The pharmacokinetics of ubrogepant are well suited to do this. Ubrogepant is rapidly absorbed and long-acting. Based on an EC₉₀ of 13 ng/mL for the inhibition of capsaicin-induced dermal blood flow (a pharmacodynamic measure of CGRP blockade), potentially effective concentrations of ubrogepant are achieved within 15 minutes and last 15 hours after a single dose of ubrogepant 100 mg (AHS poster presentation, Dodick 2019).

Treating a migraine during the prodrome may also be optimal from a practical perspective, as prodromal symptoms start well before the headache phase, thus providing patients with ample time to identify these symptoms and administer treatment, while also allowing the treatment sufficient time to act to reverse the neurobiological mechanisms that cause migraine. Ubrogepant

may be particularly well suited for administration during the prodrome for reasons including the unique role of CGRP in migraine pathophysiology, favorable tolerability profile, and no defined risk for medication overuse.

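### The SAP counts a PCS vital-sign value only if it falls during the qualifying prodrome event, a window that, read literally, no scheduled postdose measurement at Visit 3 or 4 can meet

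*SAP*

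**What the plan says.** SAP 9.4 gives the numerator of the vital-sign PCS table as: "The numerator will be the total number of participants with at least 1 PCS postbaseline value during the qualifying prodrome event". The denominator in the same paragraph takes participants with a usable baseline "values and at least 1 postbaseline assessment", with no limit on when that assessment was made. The section's attribution rule has no time limit either: "An assessment will be assigned to the most recently administered study intervention".

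Protocol 9.4.2.3 describes the same table without reference to an event: "The numerator will be the total number of participants with at least 1 potentially clinically significant postbaseline value".

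On measurement, protocol 8.2.2 says that vital signs "will be performed at every visit". The Schedule of Activities marks them at Visits 1, 2, 3 and 4/ET and leaves both treatment days blank. On treatment, protocol 6.3.1 says: "Study participants will have up to 60 days to treat 2 qualifying prodrome events at home with study intervention". On timing, protocol Section 8, under the Posttreatment Visit (Visit 3), says: "It can occur as early as 2 days after taking double-blind study intervention (after the 48 hour assessment has been completed". The same rule is given for Visit 4.

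**The concern.** The numerator asks for a PCS value inside a window in which the plan schedules no vital-sign measurement. The denominator counts participants by the visits that follow that window. A programmer who follows the sentence exactly would therefore exclude every Visit 3 and Visit 4 value from the numerator while keeping those participants in the denominator.

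Vital signs are one of the named safety endpoints. The rows at stake are those of SAP Table C-3: blood pressure, pulse rate, weight and the orthostatic changes. Rows at about 0% in both arms would look like reassurance about vital signs when they only reflect how the window was worded.

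**Working it through.** 1. **Visit window.** The Schedule of Activities sets Visits 3 and 4 at 4 days after the dose, −2/+4 days. Earliest: 4 − 2 = day 2 (2 × 24 = 48 hours). Latest: 4 + 4 = day 8 (8 × 24 = 192 hours). This reproduces the 2 and 8 days that the protocol states.

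2. **Length of the event.** Neither document says when a qualifying prodrome event ends, so four candidate lengths are compared with the earliest visit at 48 hours:
   - 6 hours (headache expected within 1 to 6 hours, protocol 6.3.1): gap 48 − 6 = 42 hours.
   - 8 hours (participant able to complete the eDiary, same section): gap 48 − 8 = 40 hours.
   - 24 hours (primary endpoint window): gap 48 − 24 = 24 hours.
   - 48 hours (end of diary follow-up): gap 48 − 48 = 0 hours. Only a visit at exactly 48 hours touches the boundary, and the protocol places the visit after the 48-hour assessment.

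   No permitted visit day lies inside the event under any of these lengths.

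3. **Measurements outside that schedule.** An ET visit is not tied to days 2 to 8. For a participant who treated no event or one event, it is arranged once the 60-day period has ended. Protocol Section 8 also allows unscheduled examinations with no timing rule. Such an examination could by chance fall inside an event. The literal count is therefore about zero, but not zero by necessity.

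4. **Neighbouring rules.**
   - Vital signs, SAP 9.4: numerator limited to the event; denominator and listing not limited.
   - Vital signs, protocol 9.4.2.3: no event limit.
   - Laboratory PCS (SAP 9.3.2), hepatic criteria (SAP 9.3.3) and ECG PCS (SAP 9.6.1): no event limit.
   - SAP Appendix F, which lists changes to the protocol-planned analyses: no mention of vital signs.

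5. **The alternative reading.** Suppose the phrase means the crossover period of that event. The second blister card is dispensed at Visit 3 (protocol 6.3), so Visit 3 precedes the second dose. Visit 3 then belongs to the first dose and Visit 4 to the second. For a participant who completes both events, 2 of 2 scheduled postdose sets are eligible on this reading and 0 of 2 on the literal one.

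**The case against.** The best counter-argument is that the phrase was never meant as a clock. Both documents use the first and second qualifying prodrome event as column labels for the two periods (SAP 2.3, protocol Table 6-2), and SAP 8.3.3 says that the repeated measurements correspond to the two events. The attribution sentence in SAP 9.4 also presupposes that clinic values belong to a dose. On that view the numerator means a PCS value in that event's period, and nothing is lost. This is a plausible account of the intention, but it does not settle the text. The word during sets a time limit, and the event has its own definition in protocol 6.3.1. The SAP's adverse-event rules (9.2.1) name Period 1 and Period 2 when periods are meant. The attribution sentence decides which treatment a value belongs to; it does not widen the numerator.

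A second argument is that the cases would remain visible. This stands. SAP 9.4 also requires a listing of participants with PCS postbaseline values, without an event limit, and summaries at each postbaseline timepoint. Under protocol 10.3.1, vital-sign findings judged clinically significant are adverse events. A near-empty table beside a populated listing would probably be noticed, but the two outputs would still contradict each other.

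A reader might go further and infer that the numerator is empty by construction, or that the report would necessarily declare no PCS vital signs. The documents do not support either: unscheduled examinations are allowed, ET visits are not bound to days 2 to 8, the period reading is open, and the listing is unrestricted.

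**Conclusion.** The numerator rule is wrong as written. Taken literally, it excludes every scheduled Visit 3 and Visit 4 value and would give PCS percentages of about 0% in both arms, whatever was observed at those visits. It also conflicts with its own denominator, with protocol 9.4.2.3 and with the SAP's parallel laboratory and ECG rules, and the departure is not declared in Appendix F. The conclusion rests on the literal reading and on an event lasting no longer than the 48-hour diary follow-up. Under the period reading the table works, but the SAP does not state that reading.

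The reach is limited to one descriptive safety table. Efficacy, sample size and type I error are untouched. A count of omitted participants would be tempting, but the documents give no PCS rate and no expected number of treated participants per intervention in the safety population. The 480 in SAP 2.4 is the effective total sample size for the primary endpoint.

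A reader might also infer that the visit values say nothing about drug effect, because protocol 2.1 states that "potentially effective concentrations of ubrogepant are achieved within 15 minutes and last 15 hours after a single dose of ubrogepant 100 mg" and the visits start at 48 hours. That concerns the visit schedule, not the numerator. Any figure for residual concentration would need a half-life that the documents do not give, so it forms no part of this point.

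**What to change.** In SAP 9.4, replace the event restriction so that the numerator is the number of participants with at least one PCS postbaseline value after the dose of that period and before the next dose, if any. Keep the section's existing rule that assigns each assessment to the most recently administered intervention. This restores the protocol 9.4.2.3 numerator and makes the period allocation explicit, which simply deleting the phrase would not do. If the restriction was intended, the SAP should define when an event ends, apply the same limit to the denominator, and list the change in Appendix F.

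The cost is one phrase in the SAP and the matching table specification. No new data are needed. The reported percentages may become non-zero and would then agree with the listing.
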